2.5 INTERVENTION ASSIGNMENT AND RANDOMIZATION/STRATIFICATION PROCEDURES

2.5.1 Cohort

Number	Name	Description
1	Patients	Patients with a diagnosis of a high-grade or high-risk cancer with active disease and poor prognosis.
2	Parents	Parent or adult primary caregiver of patient participants.

2.5.2 Arms

Number	Name	Description
1	EMI Group	Participate in an in-person session followed by a series of at-home assignments, and two “booster” sessions.
2	Control Group	Participants will briefly meet with a member of the research team who will assess parent and child coping, and provide the child-caregiver dyad educational material about coping with cancer

2.5.3 Stratifications

Name	Distinct Options	Notes
Adolescents	Yes: 13-17 years old No: 5-12 years old	
Young Adults	Yes: 18-24 years old No: > 18 years old	

2.5.4 Randomization and Arm Assignment

Patients, cohort 1, will be randomized between arms 1 and 2 stratifying for age. Once randomization of the patient has occurred their parent or primary caregiver, cohort 2, will be directly assigned to the arm in which their child was assigned.

2.6 BASELINE EVALUATION

Following parental consent and child assent, the parent/caregiver (see **Table 1**) and the participant (see **Table 2**) will complete a baseline assessment (Time 1) including questionnaires that assess their stress, emotional (e.g., depression, anxiety) and physical (e.g., pain, fatigue) wellbeing, in addition to baseline mindfulness/self-compassion. Disease parameters (e.g., cancer type and location, treatment history and radiation/chemotherapy doses, steroid use) will be abstracted from medical records. Participants will then be randomized to the enhanced mindfulness intervention (n=10 dyads) or a psychoeducation control group (n=10 dyads). The experimental design is depicted in **Figure 1**.

[figure not shown]

Figure 1 (See the Study Instrument 1 for descriptions of the measures).

2.6.1 Measures assessing caregiver (parent) functioning:

1. Demographic Questionnaire (5 minutes)

(see Study Instrument 1 for additional information regarding measures)

Table 1: Measures assessing parent functioning

Study Variable	Measure	Time Point	Time to Complete (approximate)
Self-compassion	The Self-Compassion Scale	All	10 minutes
Acceptance	Illness Cognition Questionnaire	All	< 5 minutes

Study Variable	Measure	Time Point	Time to Complete (approximate)
Mindfulness skills	Mindful Attention and Awareness Scale (MAAS)	All	5 minutes
Emotional well-being	PROMIS Emotional Distress: Anxiety and Depression, Short Forms 8a	All	5 minutes
Physical well-being	PROMIS Fatigue and Sleep Disturbance, Short Forms 6a	All	< 5 minutes each
Affect	Positive and Negative Affect Scale	All	5 minutes
Coping	Coping Inventory	All	<5 minutes
Feasibility	Feasibility Survey	Post-EMI	5 minutes
Total amount of time at each assessment			~ 35 minutes

2.6.2 Measures assessing Patient Functioning

(see Study Instrument 1 for additional information regarding measures)

Table 2: Measures assessing patient functioning

Study Variable	Measure	Time Point	Time to Complete (approximate)
HRQL	Impact of Pediatric Illness (IPI), self- and caregiver-report (ages 5+)	All	10 minutes
Mindfulness skills	Child and Adolescent Mindfulness Measure (CAMM), self-report (ages 8+)	All	5 minutes
Emotional wellbeing	PROMIS Emotional Distress: Anxiety and Depression, self-report (ages 8+) and caregiver report (ages 5+)	All	< 5 minutes
Physical wellbeing	PROMIS Pain Behavior, Short form 8a, self-report (ages 8+) and caregiver report (ages 5+)	All	< 5 minutes
Physical wellbeing	Neuro-QoL Fatigue, short form, self-report (ages 8+)	All	< 5 minutes
Physical wellbeing	PROMIS Fatigue, short form 8a, caregiver report (ages 5+)	All	<5 minutes
Affect	Positive and Negative Affect Scale – Child Shortened version	All	<5 minutes

Feasibility	Feasibility Survey, self- and caregiver-report (ages 5+) 
• Patient participant ages 5-7 (interview with 3-point Likert scale)• Patient participant ages 8+ (5 point Likert scale)	Post-EMI	5 minutes
	Total amount of time at each assessment for child participants ages 8+	~ 30-35 minutes	
	Total amount of time at each assessment for child participants ages 5-7	~ 10-15 minutes	
	Total amount of time at each assessment for caregiver-proxy report	~20-25 minutes	

3 STUDY IMPLEMENTATION

3.1 STUDY DESIGN

This is a pilot trial that principally aims to evaluate the feasibility of a novel EMI for children and young adults with high-grade/high-risk cancers and their caregivers. Secondarily, through the use of a pilot randomized-controlled design, this trial will examine the preliminary efficacy of the EMI (n=10 dyads [patient participant and parent/primary caregiver]) compared to a psychoeducation control (n=10 dyads). This study design was chosen because randomized pilots provide both feasibility and preliminary efficacy data, which are essential for justifying larger trials and/or evaluating limitations of the intervention.

At baseline, all participants will complete a series of measures assessing their functioning including emotional (e.g., depression, anxiety, stress) and physical (e.g., pain, fatigue) wellbeing, positive and negative affect, coping, and mindfulness/self-compassion.

Patient-parent/caregiver dyads will be randomized to one of two groups: the EMI group or the psychoeducation control group. The EMI group will participate in an in-person session followed by a series of at-home assignments, and two “booster” sessions. At the conclusion of the EMI, measures will be repeated (8 weeks post-baseline: Time 2), and again at 16-weeks post-baseline (Time 3). At the 8 week timepoint, the EMI group will also complete a measure of feasibility, which is a primary outcome for this study. Measures will be administered either with paper forms or electronically via iPads in clinic, or from participants’ home computer. Caregiver forms will take approximately 30-35 minutes to complete. For children \geq 8 years old and young adults, questionnaires will take approximately 30-35 minutes to complete. Children 5-7 years old will complete an abbreviated set of questionnaires (i.e., 10-15 minutes), given the limited availability and reliability of self-report measures in this age group.

Upon randomization to the psychoeducation group, patient participants and their parent/primary caregiver will briefly meet with a member of the research team who will assess parent and child coping, and provide the child-caregiver dyad educational material about coping with cancer (see Study Instrument 2). One of the psychologists will call or videochat with the family at 1 week and 3 weeks post-baseline to be consistent with the EMI group, although these phone contacts are not expected to take as long as in the EMI group. If more intensive services are needed, the patient will be taken off study and the research team will continue to provide more frequent mental health services as needed. At the conclusion of 8 weeks and completion of the measures (Time 2), the psychoeducation group will be offered the opportunity to participate in the EMI. If

participants in the psychoeducation group would like to participate in the EMI but travel to the NIH presents a hardship, the option will be made available to complete the EMI training via videochat and materials will be sent via postal mail.

The final set of questionnaires (i.e., Time 3) will be administered to parents and children in both the EMI and the psychoeducation group 16-weeks post-baseline. This time point will be used to evaluate the longer-term outcomes among patients and caregivers and to track functioning over time. It will also provide additional post-EMI data for any dyads from the control condition that electively enrolled in the EMI at Time 2. If a participant in either the EMI group or control group exhibits significant clinical disease progression after enrollment, such that they are no longer able to participate in the intervention and/or complete study-related questionnaires, they will be taken off study. If this were to occur, caregivers would be offered the option of remaining on study to complete the intervention. If patients are taken off-study before the 8-week time point due to disease progression and cannot be evaluated, they will not be included in the target *N* and can be replaced by a new participant.

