1 INTRODUCTION

1.1 STUDY OBJECTIVES

1.1.1 Primary Objective

To assess the feasibility and acceptability of an enhanced mindfulness intervention in children (ages 5-17) and young adults (ages 18-24) with a high-grade or high risk cancer and one of their primary caregivers. Feasibility and acceptability will be evaluated based on the following:

- A. Proportion of eligible dyads who enroll during a two-year period
- B. Treatment specific retention among all randomized participants, with a target retention rate of 70% over the 8 week EMI/control period
- C. Compliance with at-home practices, with a proposed target rate of 4 out of 7 days per week on average over the 8 week EMI period
- D. Parent and patient reports of satisfaction on the feasibility questionnaire; for youth ages 8+ and caregivers, average item scores >3.0 will be deemed to reflect adequate feasibility

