6.2 SAMPLE SIZE DETERMINATION

Sample size determination was not undertaken for this protocol because it is a small pilot intervention primarily aiming to test the feasibility of the proposed EMI. We specifically aimed to recruit 10 dyads per arm because this sample size would provide enough subjects to yield data appropriate for a pilot study. It is also anticipated that this sample can be recruited within a reasonable amount of time, over a 2 year period (1 to 2 dyads per month, on average). The proposed sample size will likely limit the ability to evaluate preliminary efficacy, which is an exploratory aim.

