6.3 POPULATIONS FOR ANALYSES

For the primary outcome of feasibility, all randomized participants will be included. In addition, as described below in section **6.4.2**, we will track total number of eligible individuals approached about the intervention (prior to randomization/enrollment), which will allow us to evaluate the proportion of eligible dyads who enroll. To evaluate exploratory aims, a modified intent-to-treat dataset will be used and will include all participants who, at a minimum, complete the initial in-person training (across EMI and psychoeducation conditions) and questionnaires at Time 1 (baseline) and Time 2 (8 weeks).

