6.4.2 Analysis of the Primary Endpoints

Planned analysis: For the primary feasibility aim, descriptive and summary statistics will be used to report parent and child rates of intervention completion, as well as ratings of satisfaction with the intervention via responses on a feasibility questionnaire. A Z-test for binomial proportion with continuity correction will be used to examine whether the retention rate and at-home practice compliance rate are lower than the target (i.e., respectively, a target of 70% participants retained over 8 weeks and a practice rate of 4 out of 7 days per week on average over 8 weeks). Retention rate will be evaluated across the experimental and control groups, and separately for each. In addition, descriptive and summary statistics will be used to detail the total number of patients screened, determine rates and reasons for non-eligibility and patient refusal, the number and type of adverse events (if any), and the number of days practiced (obtained via text/email) by each participant. A series of t-tests (for continuous variables) and Chi-square tests (for non-continuous variables) will be used to examine potential differences between eligible patients who accept or decline study participation; between participants who meet (versus do not meet) the target practice rate (i.e., 4 out of 7 days completed); and for other medical, psychological, and contextual factors. Nonparametric models will be used if data do not meet assumption checks.

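### Does replacing a patient who progresses, while the caregiver stays on study, leave the primary retention rate without a usable definition?

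*Combined protocol and SAP*

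**What the plan says.** **Replacement (Section 3.1).** Patients taken off study before week 8 because of "disease progression and cannot be evaluated, they will not be included in the target *N* and can be replaced by a new participant". When a patient is taken off for progression, "caregivers would be offered the option of remaining on study to complete the intervention".

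**Retention (Sections 1.1.1 and 6.1.1).** The second of four feasibility measures is "Treatment specific retention among all randomized participants, with a target retention rate of 70% over the 8 week EMI/control period".

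**Population (Section 6.3).** "For the primary outcome of feasibility, all randomized participants will be included".

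**Test (Section 6.4.2).** A continuity-corrected Z-test compares the retention rate with "a target of 70% participants retained over 8 weeks", over both groups together and for each group. The same section reports completion rates for parents and for children descriptively.

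**Unit.** Section 2.5.1 lists patients and parents as two cohorts. Section 2.5.4 randomizes the patient, and then: "Once randomization of the patient has occurred their parent or primary caregiver, cohort 2, will be directly assigned to the arm" the child received. Section 3.1 puts it as "Patient-parent/caregiver dyads will be randomized to one of two groups". Section 3.4.2, on compensation, treats each child and each caregiver as a participant.

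**Size and status.** Section 6.2: "We specifically aimed to recruit 10 dyads per arm", with no formal sample size calculation. Section 6.1 says that the primary aim involves no hypothesis testing, and Sections 6.1.1 and 6.4.1 treat any test results as descriptive.

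**The concern.** Two things look wrong on a first reading.

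First, if the phrase *target N* meant the analysis denominator, every patient lost to progression would vanish from the retention rate and be replaced by someone with a fresh chance of being retained. That would inflate a primary measure, and it would conflict with the all-randomized population in Section 6.3.

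Second, Section 3.1 itself creates dyads in which one member has left and the other continues. Such a dyad scores 0 of 1 if patients are counted, 1 of 2 if individuals are counted and 1 of 1 if caregivers are counted. Section 6.4.2 does not say which count is set against 70%. Progression is foreseeable in patients with active disease and a poor prognosis, so the case is not far-fetched. If the unit were picked after the data were seen, the same trial could be reported as above or below its own benchmark, and that benchmark is meant to inform a larger trial.

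**Working it through.** **1. The denominator.** Sections 1.1.1, 6.1.1 and 6.3 each take all randomized participants and make no exception for replaced patients. In Section 3.1 *target N* appears in the same sentence as the permission to replace, and Section 6.2 presents 10 dyads per arm as a recruitment aim. If *target N* is the accrual count, every passage agrees: the replaced patient no longer counts toward 10 + 10 = 20 dyads but stays in the retention denominator. If it is the analysis denominator, Section 3.1 contradicts three other sections. The first reading is the natural one.

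**2. The unit.** Sections 1.1.1 and 6.1.1 speak of dyads for enrolment but of participants for retention. No section proposes a dyad-level retention rate. Sections 2.5.4 and 3.1 describe the same act, because the caregiver always follows the patient's arm. The open choice is therefore patients versus individuals.

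**3. How far the choice moves the estimate.** The documents give no progression rate, so these inputs are assumptions: 23 dyads randomized, 3 patients replaced, both members retained in 16 dyads, neither in the other 23 − 16 − 3 = 4. Let c be the number of the 3 caregivers who stay (0 to 3).

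| Count | Formula | c = 0 | c = 3 |
|---|---|---|---|
| Patients | 16/23 | 69.6% | 69.6% |
| Individuals | (2×16 + c)/46 | 69.6% | 35/46 = 76.1% |
| Caregivers | (16 + c)/23 | 69.6% | 19/23 = 82.6% |

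Dropping the replaced patients, which Section 6.3 does not allow, would give 16/20 = 80.0%.

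**4. Whether the test result changes.** z = (|x − 0.7n| − 0.5)/√(0.21n), set to 0 when the numerator is negative; two-sided p as in Section 6.4.1.

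- 16/23: |16 − 16.1| − 0.5 < 0, so z = 0 and p = 1.00.
- 35/46: (2.8 − 0.5)/3.108 = 0.74, p = 0.46.
- 19/23: (2.9 − 0.5)/2.198 = 1.09, p = 0.275.
- 16/20: (2.0 − 0.5)/2.049 = 0.73, p = 0.46.

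**5. A wider range.** The same test was run with 14, 15 or 16 of 20 evaluable dyads retained and 0, 2, 4 or 6 further dyads replaced. Each replaced dyad was counted in turn as excluded, not retained, retained through the caregiver, or as two individuals with one retained. For 16 retained and 4 replaced, the rates are 16/20 = 80.0%, 16/24 = 66.7%, 20/24 = 83.3% and 36/48 = 75.0%, with p = 0.46, 0.89, 0.23 and 0.55. Over the whole grid the smallest two-sided p is 0.113 (14/26 = 53.8%). Section 6.4.2 asks whether the rate is lower than target; the smallest lower-tail p is 0.057, for the same 14/26. Per arm, with 7 or 8 of 10 retained and 0 to 3 replaced, the smallest two-sided p is 0.333. For scale, the two-sided test falls below 70% only at 9/20 or fewer overall, or 3/10 or fewer in one arm.

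**6. A separate matter: clustering.** If half of 20 dyads were retained, both members together, 10/20 gives z = (10.5 − 14)/2.049 = −1.708, p = 0.088, while 20/40 gives z = (20.5 − 28)/2.898 = −2.588, p = 0.010. This shows why linked members should not be pooled as independent. It involves no replaced patient and no split dyad, and the plan nowhere says that it pools them.

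**The case for a change.** The best case for a change is that retention is a primary measure with a numeric target, the plan itself provides for the split dyad, and a short clarification would close the gap at almost no cost. The parent and child reporting in Section 6.4.2 concerns completion rates, whereas the Z-test sentence refers to a single retention rate, split only by arm. Section 3.1 says pilot data are needed to justify larger trials, so a loosely defined rate has a later cost even without a formal decision here.

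Part of this stands. No section defines retained, names the unit of the tested rate, or says how a continuing caregiver counts. The point estimate can also fall on either side of 70%, as step 3 shows.

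The rest does not carry. The denominator rule is already written. No stated rule produces a wrong number; a definition is simply not spelled out. Off-study status is tracked by participant (Sections 2.4 and 3.5), patients and caregivers are separate cohorts, and Section 6.4.4 lists individual data by measure and time point, so split dyads should be visible to whoever reads the results. That the unit would be chosen to suit the data is a possibility, not something that follows from the plan.

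**Conclusion.** The concern does not call for a change. Replaced patients remain in the retention denominator under Sections 1.1.1, 6.1.1 and 6.3, and *target N* in Section 3.1 is best read as accrual only. The remaining gap is a missing definition that a competent analyst fills in the obvious way: patient and caregiver retention as two rates, each over all dyads whose patient was randomized, with one observation per dyad in any test and the number replaced stated.

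In the 23-dyad illustration the choice of count moves the estimate by at most 82.6 − 69.6 = 13.0 percentage points. No test result changed there or anywhere in the wider range examined. The replacement and retention counts are assumptions, since the documents give none; a trial with much heavier progression could show larger differences. The conclusion also rests on the plan's own position that these results are descriptive and on the absence of any go/no-go rule tied to 70%. If retention became a formal progression criterion for the larger trial, the unit would have to be fixed in advance there.

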3.2 IN-PERSON SESSION

3.2.1 Enhanced Mindfulness Intervention Group

The in-person session for the EMI group will be scheduled to coincide with an already scheduled clinic visit whenever possible. Dyads assigned to participate in the mindfulness intervention will be paired with two members of the clinical research team (i.e., two psychologists/psychology associates trained in mindfulness-based interventions, referred to as “mindfulness coaches”). Following completion of the baseline measures, the child participant will meet with one member of the research team for an initial training session, while the parent participant will have a concurrent training session with the second member of the research team.

The initial in-person session will last 75-90 minutes, and child and parent sessions will follow the same format. Specifically, the session will include a brief interview to build rapport and to further assess overall wellbeing, sources of stress (related and unrelated to cancer), and existing coping strategies (15-20 minutes). Subsequently, using developmentally-appropriate language and exercises, mindfulness will be introduced and practiced (30 minutes), followed by a discussion of personally-relevant values and goals (20 minutes) in which the mindfulness practice can be contextualized and individualized for each participant.

The parent and child participant will come together for the final 15 to 20 minutes of the training session. This time will afford an opportunity to teach parents about the mindfulness practices assigned to their children and allow dyads to participate in a joint mindfulness exercise.

Given the broad age range of this intervention, the interview style and exercises utilized for the in-person training sessions will be unique for each age group of young children, adolescents, and parents (separate semi-structured manuals will be used to guide in-person sessions for children ages 5-7, 8-12, 13-24 years old, and parents, while maintaining consistency in the format across age groups). For example, the mindfulness coach will rely on interactive exercises and playful language to ascertain information from younger children during the interview (e.g., use caricatures to represent feelings when talking about stress) and to introduce mindfulness (e.g., create a “mindfulness jar” to represent the concept of mindfulness). In contrast, with adolescents and parents, the sessions may be more heavily weighted toward traditional verbal discussion/instruction. Flexibility will be permitted to adapt explanations based on a participant’s developmental stage and breaks will be offered when needed. Note: While mindfulness practices will be based on age/development, they will be standardized in length (i.e., approximately 15

minutes) and will utilize similar themes (e.g., mindful breathing, body awareness) across participants.

Following the in-person session, parents and children will be asked to practice mindfulness exercises at least 4 out of 7 days per week (see Section 3.3 for Home-Based Mindfulness Exercises). To facilitate at-home practice, each child and parent participant will receive a series of 4 exercises, lasting approximately 15 minutes each. Participants are given leeway to choose among these exercises throughout the duration of the intervention and the research team will track which exercises are practiced throughout the week. For parents, at-home practice will consist of .mp3 audio files with guided mindfulness practices. Youth participants will receive multiformat exercises (e.g., age-appropriate .mp3 audio files, art-based exercises, interactive games that can be done with the assistance of a caregiver or sibling). Several mindfulness practitioners and researchers have developed exercises that are for the mutual benefit of parents and children [53:54](#), which can be practiced together. Adaptations of these exercises will be provided to families of younger children (i.e., <8 years old), so as not to overburden a parent with independent practice *and* their child's practice separately. Children who are nonverbal (i.e., cannot express themselves verbally) due to their disease and/or treatment will have access to appropriate interventions that do not entail verbal skills.

Approximately one week and three weeks after the initial in-person training session, a brief (i.e., 30 minute) follow-up sessions will take place with the two-person research team. We anticipate that the majority of participants in this study will be staying at or nearby the NIH during this time period, or will be visiting the NIH frequently (e.g., receiving radiation treatment through other protocols at the NIH Intramural Research Program), which will make it possible to schedule follow-ups in person. For in-person follow-up, caregivers and children will each meet separately with their mindfulness coach, and then come together at the end of the follow-up for a joint meeting. If participants are not available for an in-person follow-up, sessions will take place via video chat (e.g., Skype, FaceTime) or telephone if video chat is unavailable. The literature suggests comparable efficacy between in person and teletherapy, which makes this a valid option [55](#). The purpose of these follow-up sessions is to troubleshoot any challenges that arise (e.g., difficulty finding time to practice) and to engage in a clinician-guided practice. Depending on the age and functional limitations of the child, remote follow-up sessions will take place jointly with the parent/child or separately. Attendance in follow-up sessions will be systematically tracked and will be evaluated as part of the feasibility of this intervention.

Throughout the intervention, weekly text messages (or emails when text is not an option) will be sent to parent participants and youth with a personal cell phone, in which we will ask individuals to indicate the number of days practiced in the past week. The following script will be used as a guideline: "Hello. Just checking in to ask how many days you have practiced mindfulness over the past week (since **INSERT DATE**). Please reply by text (or email) with your response." The weekly interval will mitigate concerns regarding inaccurate recall [56:57](#), without overburdening families. Among younger children who do not have a personal cell phone, compliance data will be collected through parents, or children (>7 years old) will be loaned an iPod (with parental permission) from the study team through which compliance data can be obtained. All participants will also be provided with an optional tracking sheet, on which they can keep track of practice days and note the specific exercises completed (Study Instrument 3).

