6.1.1 Primary Objective

The primary objective of this study is to assess the feasibility and acceptability of an enhanced mindfulness intervention in children and young adults (ages 5-24) with a high-grade or high-risk cancer and one of their primary caregivers. Feasibility and acceptability will be evaluated based on the following:

1. Proportion of eligible dyads who enroll during a two-year period
2. Treatment specific retention among all randomized participants, with a target retention rate of 70% over the 8 week EMI/control period
3. Compliance with at-home practices, with a proposed target rate of 4 out of 7 days per week on average over the 8 week EMI period
4. Parent and child reports of satisfaction on the feasibility questionnaire; for youth ages 8+ and caregivers, average item scores >3.0 will be deemed to reflect adequate feasibility

Of note, because the sample size of this study is very limited, even the results of the comparisons tested using statistical methods and identified within the primary objective will be considered descriptive and hypothesis generating.

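### The weekly text behind primary criterion C does not separate at-home practice from coach-led practice, so a few session days can be reported as compliant days

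*Combined protocol and SAP*

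**What the plan says.** Section 6.1.1 (and section 1.1.1, item C) defines the third feasibility component as "Compliance with at-home practices, with a proposed target rate of 4 out of 7 days per week on average" over the 8-week EMI period. Section 6.4.2 names the data for it: "the number of days practiced (obtained via text/email) by each participant". The same section compares the compliance rate with the target and contrasts participants who do and do not meet 4 days in 7.

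The message is in section 3.2.1. It is introduced with "The following script will be used as a guideline", and its question is "Just checking in to ask how many days you have practiced mindfulness over the past week", counted from a date that staff insert. The reply is a single number of days.

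The same section places coach-led practice inside the 8 weeks. Follow-up sessions take place "Approximately one week and three weeks after the initial in-person training session", and one of their purposes is "to engage in a clinician-guided practice". The initial session sets aside 30 minutes to introduce and practise mindfulness and closes with a joint exercise for parent and child. Follow-up attendance is tracked and assessed as a feasibility measure in its own right.

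Participants also receive a sheet for noting practice days and exercises. Section 3.2.1 calls it optional, while section 3.3 says the team will use a tracking sheet to follow which exercises are chosen.

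**The concern.** The criterion and the question do not cover the same thing. The criterion concerns practice at home. The question concerns any mindfulness practice. Someone who answers it literally and truthfully includes a day on which the only practice was with a coach, and nothing in section 3.2.1, 6.1.1 or 6.4.2 says that such a day is left out.

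This mechanism can only raise the count. The count feeds the average, the comparison with target and the split into those who meet the target and those who do not. Both members of a dyad attend the sessions, so both can be affected. A session already recorded under attendance could also add to home compliance, so one event would support two feasibility measures. The pilot is meant to show whether families keep up a brief programme that relies mainly on at-home practice, so a count that includes session days answers a slightly different question.

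**Working it through.** The plan gives no figure for this effect, so there is nothing to reproduce. The check bounds it.

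**Inputs from the documents**
- Target: 4 days per week for 8 weeks, so 4 × 8 = 32 of 7 × 8 = 56 days (section 6.1.1).
- Coach-led days: 2 follow-ups. The initial session makes 3 if the first inserted date takes in that day (section 3.2.1).
- 10 dyads in the EMI arm (section 6.2).

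**Assumptions (the documents give no values)**
- p, the chance of home practice on a given day, varied from 0.40 to 0.65, with days independent.
- Every session day is reported as a practice day.

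**Step 1: maximum inflation.** This applies if there is no home practice on session days.
- 2 days: 2/8 = 0.25 days per week, and 2/32 = 6.25% of the target.
- 3 days: 3/8 = 0.375 days per week, and 3/32 = 9.4% of the target.

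**Step 2: expected inflation.** A session day adds to the count only if there was no home practice that day, so the expected inflation is c(1 − p)/8 for c session days.
- p = 3.75/7 = 0.536: 2 × 0.464/8 = 0.116; 3 × 0.464/8 = 0.174.
- p = 4/7 = 0.571: 2 × 0.429/8 = 0.107; 3 × 0.429/8 = 0.161.

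The range is about 0.11 to 0.17 days per week. If only half the sessions are reported, it halves.

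**Step 3: who can change class.** A reported total of 32 needs at least 32 − 2 = 30 true days (30/8 = 3.75 per week), or 32 − 3 = 29 (29/8 = 3.63 per week). Only totals of 30 to 31, or 29 to 31 with the initial session, can move. For example, 30 true days plus 2 session-only days is reported as 32, or 4.00 per week.

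**Step 4: chance that one participant reaches 32 days.** Without session days this is P(Bin(56, p) ≥ 32). With c session days always counted it is P(Bin(56 − c, p) ≥ 32 − c).

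| p | Home days only | 2 session days counted | 3 session days counted |
|---|---|---|---|
| 0.40 | 0.007 | 0.015 | 0.021 |
| 0.50 | 0.175 | 0.248 | 0.292 |
| 0.55 | 0.427 | 0.524 | 0.573 |
| 4/7 | 0.556 | 0.647 | 0.691 |
| 0.65 | 0.914 | 0.943 | 0.955 |

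The largest shift is about 10 percentage points with 2 days and about 15 with 3, for people already near the threshold.

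**Step 5: group mean of 10 participants.** This simulation lets p vary between people (beta distribution), with an assumed mean of 3.75 days per week and between-person SD of 1.5. Home practice continues on session days at each person's usual rate.
- Chance that the group mean reaches 4.0: 0.31 on true days, 0.40 with 2 session days always reported, about 0.44 to 0.45 with 3.
- Participants wrongly classed as meeting the target: 2.5% with 2 days, 3.8% with 3.

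The assumed mean lies just below the target, where the effect is most visible. The standard error of the mean is 1.5/√10 = 0.47, so a shift of 0.116 is about a quarter of one standard error.

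**The case against.** The strongest reply is that the documents show only that session days could be reported, not that they will be. The script is a guideline, and it follows an instruction to practise assigned exercises after the in-person session, so many participants will understand what is meant. That stands: the point is a gap in the wording, not a demonstrated miscount.

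It is also fair that little depends on the result. Sections 6.1.1 and 6.4.1 declare the feasibility comparisons descriptive, and no decision rule is attached to criterion C.

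A reader might infer that the criterion requires unsupervised practice. The documents do not say so. Section 3.3.4 has children aged 5 to 7 practise with a caregiver, and follow-ups may be held by video or telephone, so some coach-led practice may physically take place at home. Whether such a day counts is a choice the plan has to make. This is a reason to state the rule, not evidence of error.

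A reader might also infer that the count cannot be repaired afterwards because only weekly totals are collected. That is too strong. Follow-up attendance is tracked, so the true count can be bracketed, although weekly totals alone do not show whether home practice also took place on a session day. The tracking sheet may help, but the instrument is not in the documents and section 3.2.1 makes it optional.

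**Conclusion.** The point holds as a minor measurement gap. The question put to participants is wider than criterion C, coach-led practice falls within the reporting period, and no rule excludes it. Any resulting bias is upward.

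The caps of 0.25 and 0.375 days per week follow from the session schedule alone. The expected values of about 0.11 to 0.17 rest on assumed practice near 3.75 to 4 days per week and on every session being reported. The effect is zero for anyone who also practises at home on session days or who leaves sessions out of the reply.

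The tempting stronger conclusion is that session days do count and carry borderline participants over the target. The documents do not support it: they are silent on how session-only days are treated, and only participants with 29 to 31 true days could be affected. The change is still worth making, because it concerns a primary measure and costs almost nothing.

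**What to change.** - **Section 3.2.1, message.** Ask on how many of the past 7 days the person practised the assigned exercises on their own or with family, wherever they were staying, not counting practice done with a coach during a session, whether in person or remote. Simply adding the words *at home* would not be enough. Section 3.2.1 expects most families to be staying at or near the NIH or visiting often, and section 3.4.2 expects some to be away from home. A literal reader would then leave out valid independent practice, which could remove more days than the sessions add.
- **Section 6.4.2.** State that criterion C counts only these days.
- **Replies already collected with the present wording.** Report the raw count as an upper bound. Report the count minus attended session days as a lower bound, including the initial session only where the first inserted date takes in that day. The subtraction is a bound and not a correction: it removes a valid day whenever the person also practised independently on a session day or never reported the session. Both bounds take the replies as otherwise accurate.

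The cost is a slightly longer message, one clause in section 6.4.2 and a count from attendance data already tracked. The compliance figure may be slightly less favourable. No visit or procedure is added.
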